3.3 Efficacy Co-Primary Trial Hypothesis

3.3.1 The Hodges-Lehmann Estimate

We denote the set of observed MLAs for subjects $i = 1, 2, \dots, n_j$ in Group $j = 1$ (IMVAMUNE followed by ACAM2000 group) and Group $j = 2$ (ACAM2000 only group) as $x_{i,j}$. The observed sample median is denoted

$$\tilde{x}_j = \frac{1}{2} (x_{(\lfloor (n_j+1)/2 \rfloor)} + x_{(\lceil (n_j+1)/2 \rceil)})$$

where $\lfloor (n_j + 1)/2 \rfloor$ is the floor, or integer part of w rounded down, and $\lceil (n_j + 1)/2 \rceil$ is the ceiling, or integer part rounded up. In the case of an even value of n_j then the floor and ceiling are the same value. The bracket notation $x_{(k)}$ denotes the k -th largest value in the set, or k -th order statistic, where $x_{(1)}$ and $x_{(n)}$ are the minimum and maximum values respectively.

Here we wish to calculate the confidence interval of the ratio of the medians, i.e. $r = \tilde{x}_1/\tilde{x}_2$. The usual method of calculating the confidence interval of the ratio of the medians is to consider the logarithm of difference in the medians, i.e. $\log(r) = \log(\tilde{x}_1) - \log(\tilde{x}_2)$ and to calculate the confidence interval of the difference and then to take the antilogarithm to obtain the confidence interval for the ratio of medians. However, this presents problems due to possible zero values in the lesion area data. In fact, it is even possible that the median of Group 1 may be zero. To counteract this issue a small offset of 1 will be added to each zero value and the AREA Attenuation Rate (AAR) is calculated as:

$$AAR = 1 - \frac{\tilde{x}_1}{\tilde{x}_2} = 1 - r \quad (1)$$

By subtracting the median ratio from 1 the AAR reflects the reduction in MLA.

Defining $y_{i,j} = \log(\max\{1, x_{i,j}\})$. It is assumed that $Y_{i,j}$ are independent identically distributed random variables from a continuous distribution, i.e.

$$\Pr(Y_{i,j} < u) = F_j(u) \quad (2)$$

Similarly, we denote the MLDs (maximum lesion DIAMETERs) for subjects $i = 1, 2, \dots, n_j$ in Group $j = 1, 2$ as $u_{i,j}$, with $v_{i,j} = \log(\max\{u_{i,j}, 1\})$, with zero MLD measurements replaced by 1 (as for the AAR calculations). The DIAMETER Attenuation Rate (DAR) is then:

$$DAR = 1 - \frac{\tilde{u}_1}{\tilde{u}_2}$$

Because no data has currently been confirmed for the MLA, it is not clear what the distribution of the MLA will be, and therefore it is sensible to use a non-parametric method.

For the HL method which will be used here, it is further assumed that both groups have the same distribution function but this has been shifted by an offset Δ for Group 2. This is referred to as the homogeneity of distribution assumption, i.e.

$$F_1(u) = F_2(u - \Delta) \quad (3)$$

Next we define the set of $n_1 \times n_2$, so called, Wald differences as:

$$d_{ij} = (y_{i1} - y_{j2}) \quad \forall i, j$$

For current purposes an estimate of the shift difference is needed. The HL estimator (Hollander, 2014) is typically used to estimate the shift. Basically, the median of the Wald differences makes a very efficient estimator of the shift parameter, i.e.

$$\hat{\Delta} = \tilde{d} \tag{4}$$

The Mann-Whitney test statistics, denoted U , is defined as the number d values below zero. The U statistic which has the following expectation and variance under the assumption that $\Delta=0$:

$$E[U] = \frac{1}{2} n_1 n_2$$

$$V[U] = \frac{n_1 n_2 (n_1 + n_2 + 1)}{12}$$

One advantage of the HL estimate is that it has a straightforward way to estimate a $100(1-\alpha)\%$ confidence interval denoted $(\hat{\Delta}_L, \hat{\Delta}_U)$ attributed to Lincoln Moses (Hollander, 2014).

We specify the order statistics of the set of Wald differences as $\{d_{(1)}, d_{(2)}, \dots, d_{(n_1 n_2)}\}$, then based on a large sample size approximation to the normal distribution we find the 95% lower and upper confidence limit of U , called k_L and k_U respectively, as

$$k_L = \left\lceil E[U] - 1.96\sqrt{V[U]} \right\rceil \quad \text{and} \quad k_U = \left\lfloor E[U] + 1.96\sqrt{V[U]} \right\rfloor$$

Since this is a discrete distribution, the point k is actually the integer that just exceeds the upper confidence limit of U . Then we match the corresponding values of $(d_{(k_L)}, d_{(k_U)})$ as the estimate of the confidence interval.

The exact distribution of U (and hence k) can be found, but this can be computationally intense for large sample sizes, and the above normal approximation is then very accurate.

In general the HL estimator is estimating the shift Δ (although under the homogeneity of distribution assumption this should be the same as the difference in the two medians). The HL estimator has excellent efficiency and is at least 86.6% (Hollander, 2014) as efficient as any other estimator of the shift parameter. Even in the case that the data are normally distributed, which would be a very efficient parametric model, the HL estimator is 95.5% as efficient as the student t-test. However, when the data is not normally distributed it can be much more efficient than the mean difference estimator.

The HL estimator is also much more efficient than the median difference estimator which is rather insensitive (Høyland, 1965). The HL estimator is usually used, as here, as an estimator of the difference in the group medians. However, for comparison the HL estimator of the shift will also be presented. In addition, a secondary supportive analysis based on the PB method, which directly estimates the difference in the medians will also be presented (see below).

3.3.2 Efficacy Hypothesis

The efficacy co-primary hypothesis of the trial is to assess if the median MLA in Group 1 is reduced compared to that in Group 2. This is done by considering the AAR defined in Equation (1), and whether this is significantly greater than or equal to a pre-specified factor $\lambda=0.4$:

$$H_0: AAR \leq \lambda \quad \text{versus} \quad H_1: AAR > \lambda \quad (5)$$

This is tested using the anti-log of the 95% HL confidence interval (Lehmann, 1975) defined in Equation (4). Specifically, only the upper 95% confidence interval of the HL shift estimator is used with a one-sided significance level of 2.5%, and this needs to be below $(1-\lambda)=0.6$ for the null hypothesis to be rejected, and thus the co-primary endpoint will be met. Otherwise, the null hypothesis will not be rejected and the co-primary endpoint will not have been met. However, for completeness the anti-logs of the upper and lower confidence limits along with the point estimate of the shift estimator, and ratio of the medians will be reported.

3.3.3 Justification of λ

The value of λ is defined to be 40%, in other words so that a significant relative reduction of MLA of at least 40% in Group 1 compared to Group 2 is shown. The 40% reduction is considered a clinically significant difference as this is the level of reduction that has been seen in subjects previously vaccinated with Dryvax[®] and then revaccinated with a first generation smallpox vaccine (Wetvax) (Talbot, 2006). In this trial, 48 vaccinia-naïve subjects and 54 vaccinia-experienced subjects were vaccinated with Wetvax and treated with one of three different bandages (Gauze, Occlusive or Foam). The focus of the trial was to determine if the choice of bandage had an effect on the development of the subsequent take with a view to reducing possible re-infection rates. One of the take, or lesion, parameters measured was the maximum lesion area measured during the 14 days post scarification. The use of naïve and experienced subjects allows the comparison of the maximum lesion diameter obtained for naïve and experienced subjects. Since first generation smallpox vaccines are considered to give lifelong protection the differences observed in lesion diameters can be used as a measure of the level of attenuation that will be obtained for protected (i.e. experienced subjects). In the Talbot trial the Gauze and Occlusive bandages gave relative reductions in the median lesion diameter that equate to a relative reduction of experienced to naïve subjects lesion area of 41.5% and 37.7% respectively (assuming lesions are circular). The foam bandage gave a relative reduction of only 11.4%. The foam bandage is very different to the bandage that will be used in this trial, and hence taking a value of 40% for λ is considered a good estimate of clinical efficacy.

3.3.4 Numerical Example

The following is an illustration of the above methods using a real numerical example. The best source of information for the distribution of the MLD data available using IMVAMUNE is from the NIH sponsored POX-MVA-002 trial (Frey, 2007). In the POX-MVA-002 trial some subjects were given either Placebo/Placebo/Dryvax[®] (P/P/D), which is Group T1 in the trial; or MVA-BN[®]/MVA-BN[®]/Dryvax[®] (M/M/D), which is called group T2 in the trial. After the Dryvax[®] vaccination, the maximum diameter of the lesion was measured at various visits, including the Day 6-8 Visit and the Day 13-15 Visit. The raw data is given in Table 3 below

Table 3 Lesion Data from POX-MVA-002 clinical trial

Treatment Group = MVA/MVA/Dryvax [®] (M/M/D) N =12				
Subject ID	MLD (mm)	log(MLD)	MLA* (mm ²)	log(MLA)
██████████	0	0	0	0
██████████	0	0	0	0
██████████	2	0.301	4	0.602
██████████	4	0.602	16	1.204
██████████	5	0.699	25	1.398
██████████	7	0.845	49	1.690
██████████	7	0.845	49	1.690
██████████	7	0.845	49	1.690
██████████	7	0.845	49	1.690
██████████	8	0.903	64	1.806
██████████	9	0.954	81	1.908
██████████	10	1.000	100	2.000
Median	7	0.845	49	1.690

Treatment Group = Placebo/Placebo/Dryvax [®] (P/P/D) N =13				
Subject ID	MLD (mm)	log(MLD)	MLA* (mm ²)	log(MLA)
██████████	9	0.954	81	1.908

██████████	10	1.000	100	2.000
██████████	10	1.000	100	2.000
██████████	10	1.000	100	2.000
██████████	10	1.000	100	2.000
██████████	11	1.041	121	2.083
██████████	12	1.079	144	2.158
██████████	13	1.114	169	2.228
██████████	13	1.114	169	2.228
██████████	15	1.176	225	2.352
██████████	17	1.230	289	2.461
██████████	20	1.301	400	2.602
██████████	20	1.301	400	2.602
Median	12	1.079	144	2.158

*MLA is imputed using the rounded value of MLD^2

The MLA was imputed by assuming it was the square of the MLD, strictly speaking if we assume the lesion is exactly circular then the area is $\frac{1}{4}\pi$ of the MLD squared. However, the factor $\frac{1}{4}\pi$ will cancel out when we consider the ratio of the medians, and so for simplicity we just use the square of the MLD.

A histogram of the MLD data is given in [Figure 1](#) below. In the figure it is clear that the data do not remotely follow a Normal distribution, as they are positive and highly skewed. Therefore a student t-test of the difference between the groups is not appropriate, and it seems prudent to adopt a non-parametric approach for calculating the AAR.

[figure not shown]

Figure 1 Histogram of MLD from POX-MVA-002

The ranked Wald differences ($d_{(i)}$) of the log MLD values generate the following set of $12 \times 13 = 156$ values given in Table 4 below. From Table 3 above the $DAR = 1 - 7/12 = 0.417$. The shift estimator of the log MLA is $\hat{\Delta} = \frac{1}{2}d_{(78)} + \frac{1}{2}d_{(79)} = -0.331$ and taking 1 minus the anti-log the asymptotic HL estimate is 0.533. This is a little different from the observed DAR, but the sample size is not large in this example.

Then $E[U] = 78$ and $V[U] = 338$, hence $k = \lceil 78 + 36.03 \rceil = 115$ and $d_{(115)} = -0.155$ with $\lceil 78 - 36.03 \rceil = 42$ and $d_{(42)} = -0.628$, with the 95% HL CI of the DAR being (0.300, 0.765).

Since the lower limit of the confidence interval is below 0.4 this would not meet the hypothesis as specified above. This is not surprising since these are lesion diameters not areas and the sample size is small.

Table 4 Wald differences of log MLD values from POX-MVA-002 clinical trial

(i)	$d_{(i)}$	(i)	$d_{(i)}$	(i)	$d_{(i)}$	(i)	$d_{(i)}$	(i)	$d_{(i)}$	(i)	$d_{(i)}$
1	-1.301	27	-0.954	53	-0.456	79	-0.331	105	-0.211	131	-0.138
2	-1.301	28	-0.954	54	-0.456	80	-0.331	106	-0.211	132	-0.125
3	-1.301	29	-0.929	55	-0.456	81	-0.327	107	-0.196	133	-0.114
4	-1.301	30	-0.875	56	-0.456	82	-0.301	108	-0.196	134	-0.114
5	-1.230	31	-0.813	57	-0.456	83	-0.301	109	-0.196	135	-0.109
6	-1.230	32	-0.813	58	-0.456	84	-0.301	110	-0.196	136	-0.109
7	-1.176	33	-0.778	59	-0.439	85	-0.301	111	-0.176	137	-0.109
8	-1.176	34	-0.740	60	-0.415	86	-0.301	112	-0.176	138	-0.109
9	-1.114	35	-0.699	61	-0.415	87	-0.301	113	-0.160	139	-0.097
10	-1.114	36	-0.699	62	-0.398	88	-0.276	114	-0.160	140	-0.097
11	-1.114	37	-0.699	63	-0.398	89	-0.273	115	-0.155	141	-0.097
12	-1.114	38	-0.699	64	-0.398	90	-0.269	116	-0.155	142	-0.097
13	-1.079	39	-0.699	65	-0.398	91	-0.269	117	-0.155	143	-0.087
14	-1.079	40	-0.699	66	-0.398	92	-0.269	118	-0.155	144	-0.079
15	-1.041	41	-0.653	67	-0.398	93	-0.269	119	-0.155	145	-0.051
16	-1.041	42	-0.628	68	-0.385	94	-0.269	120	-0.155	146	-0.046
17	-1.000	43	-0.602	69	-0.385	95	-0.269	121	-0.155	147	-0.046
18	-1.000	44	-0.602	70	-0.385	96	-0.269	122	-0.155	148	-0.046
19	-1.000	45	-0.574	71	-0.385	97	-0.269	123	-0.155	149	-0.046
20	-1.000	46	-0.531	72	-0.380	98	-0.255	124	-0.155	150	-0.041
21	-1.000	47	-0.512	73	-0.352	99	-0.234	125	-0.155	151	0.000
22	-1.000	48	-0.512	74	-0.347	100	-0.234	126	-0.155	152	0.000
23	-1.000	49	-0.477	75	-0.347	101	-0.234	127	-0.155	153	0.000
24	-1.000	50	-0.477	76	-0.342	102	-0.234	128	-0.155	154	0.000
25	-1.000	51	-0.456	77	-0.331	103	-0.230	129	-0.155	155	0.000
26	-1.000	52	-0.456	78	-0.331	104	-0.222	130	-0.155	156	0.046

For the imputed MLA the median in Group T2 (IMVAMUNE then Dryvax) is 49 and the median in Group T1 (Dryvax only) is 144, and the imputed AAR = $1 - 49/144 = 0.660$.

The difference in the log10 medians is then $1.690 - 2.158 = -0.468$, with 95% HL CI of (-1.204, -0.320). So, taking 1 minus the anti-logs the 95% CI of the AAR is (0.521, 0.937). Because the lower limit is above 0.4 the primary endpoint would have been achieved using this example.

3.4 Secondary Immunogenicity Hypotheses

The most important secondary immunogenicity objective of the trial is to assess non-inferiority of MVA-BN[®] compared to a conventional smallpox vaccine (ACAM2000[®]) in terms of antibody response at the Peak Visit, i.e. 28 days after an ACAM2000[®] vaccination and 42 days after the first MVA-BN[®] vaccination using the vaccinia-specific ELISA.

The test of non-inferiority will be applied in the same way as described above for the PRNT GMTs except it will be carried out for the ELISA GMTs, i.e. the following hypothesis will be tested:

$$H_0: m_1 - m_2 \leq -\Delta \text{ versus } H_1: m_1 - m_2 > -\Delta,$$

where Δ is the non-inferiority margin and is chosen in this trial as 0.176 on the \log_{10} titers (i.e. a factor of $2/3$ reported on the original titer scale).

In addition, two further secondary non-inferiority analyses of ELISA and PRNT titers will be conducted for the individual peak titers, i.e. for each subject in Group 1 the individual maximum titer from Visit 1 to Visit 7 will be used, and in Group 2 the individual maximum titer from Visit 1 to Visit 6 will be used. The analyses will proceed in the same way as outlined above for the PRNT and ELISA non-inferiority analyses including the use of the same respective non-inferiority margins.

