## 7 Assessment of Immunogenicity and Efficacy

### 7.1 Humoral Immune Response

Analysis of humoral immune response is planned to occur at Visit 1 (baseline measurement) through Visit 4 for both groups and additionally for the Group 1 subjects at Visit 6, Visit 7 and at Visit 10 and for Group 2 subjects at Visit 5 and 6. Baseline (i.e. Visit 1 [Week 0]), Visit 4 (Week 4) and Visit 7 (week 8) blood samples will be drawn prior to any scheduled vaccination.

The immune response measured at the Peak Visits by validated vaccinia-specific PRNT and vaccinia-specific ELISA will be used as the relevant immunologic response for the assessment of non-inferiority.

Antibody responses to MVA-BN® and ACAM2000® will be measured using a vaccinia-specific PRNT and a vaccinia-specific ELISA which were established and validated at BN. Endpoint GMT titers will be done on all subjects, independent from their baseline immune status. The tests will be performed at BN, Martinsried, Germany. All immunological clinical analysis personnel will be blinded to subject randomization details.

The methods for collection, storage and handling of lab specimens for the immune analysis are specified in a separate manual which will be provided to the investigators before enrollment. Additionally, training will be provided on the procedures during the investigator meeting and/or at the initiation visit. The protocols for the analytical tests performed are detailed in the BN SOPs listed below in the assay sections. Copies of the SOPs (from BN and the CRO), effective at the time of trial conduct will be filed in the Trial Master File.

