After revaccination, skin reactions at the ACAM2000[®] vaccination site are often less pronounced and there is more rapid progression and healing than those after primary vaccination. For the purposes of this SAP and corresponding CTP attenuation is considered to be when the takes observed in Group 1 subjects (MVA-BN[®] recipients vaccinated with ACAM2000[®]) are determined to be diminished full takes based on the median of the individually measured parameter of Maximum Lesion Areas in Group 1 subjects, in comparison to the median of Maximum Lesion Areas of takes in Group 2 subjects (ACAM2000[®] recipients).

Peak Visit:

For the purposes of this SAP, the Peak Visit is the visit with the highest expected antibody titers. For MVA-BN[®] the peak responses are considered to be at Day 42 after the first MVA-BN[®] vaccination (as described in the MVA-BN[®] Investigator's Brochure) when the subject has received two (2) MVA-BN[®] vaccinations according to the standard vaccination schedule. For ACAM2000[®] the peak responses are considered to be at Day 28 post vaccination in order to be in alignment with published data for conventional smallpox vaccines reaching a peak four weeks post vaccination (Frey, 2003; Belshe, 2004; Kennedy, 2004; Frey, 2007), which is also in full agreement with the data published for ACAM2000[®] (ACAM2000 Vaccines and Related Biological Products Advisory Committee [VRBPAC] Briefing Document, April 2007).

Individual Peak Titer:

For each subject in Group 1 the individual maximum Enzyme-linked Immunosorbent Assay (ELISA) titer from Visit 1 to Visit 7 will be used as the individual peak ELISA titer, and in Group 2 the individual maximum ELISA titer from Visit 1 to Visit 6 will be used. The individual peak Plaque Reduction Neutralization Test (PRNT) titer is then defined in the same way. Here it should be noted that although the visit numbering is a little different between groups the serum sample are taken at the same time points for Group 1 and Group 2 (no sample is taken at Visit 5 in Group 1).

Enrolled Subjects:

Subjects are considered enrolled once they have received the first trial vaccination. For this trial a vaccination means administration of either MVA-BN[®] and/or ACAM2000[®].

Trial Day:

The day of trial is calculated from the day of the first vaccination. The day of first vaccination is defined as Day 0 and the day after first vaccination is Day 1, and so on. Equally, the day before

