3.7.1 Full Analysis Set

The Full Analysis Set (FAS) consists of all subjects

- i) who had received at least one dose of trial vaccine and
- ii) for whom any post vaccination safety or immunogenicity data are available

The safety analysis and secondary supportive immunogenicity analyses will be performed on the FAS. Subjects in Group 1 who do not receive an MVA-BN[®] vaccination will not be considered enrolled in the trial (although they should receive an ACAM2000[®] vaccination outside of the protocol later).

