3.8 Definitions, Data Conventions and Handling of Missing Data

3.8.1 Missing Data

Analysis of immunogenicity variables will be done on a valid case basis, i.e. for missing observations no imputation technique such as “Last observation carried forward” (LOCF) will be applied, since this could introduce an optimistic bias into the analysis.

For the analysis of safety data incomplete AE and medication start and end dates will be imputed in order to assign these events to the correct vaccination period (see [Section 3.8.2](#)).

Missing Vital Signs data for Visit 1 will be imputed using screening (or latest re-screening) values. However, this will be displayed as ‘Baseline’ values in the tables and listing for Vital Signs data without reference to whether the data originated from Visit 1 or SCR.

All data will be listed and summarized as captured in the eCRF. However, it may be necessary to impute incomplete AE and medication start and end dates in order to assign these events to the correct vaccination period, which will be done as follows:

For prior and concomitant medication and AEs imputation of partial start and end dates will be done for analysis purpose according to the following rules:

Missing	Rule for start date	Rule for end date	Flag for imputation
Day	First of month*	Last of month*	D
Month [†]	1. January*	31. December*	M
Year [†]	no imputation	Last visit date	Y

* Unless the imputed start date is before first visit date, in which case first visit date is used; or the imputed stop date is after last visit date in which case last visit date available is used.

† It is assumed that a missing month implies a missing day as well, and that a missing year implies a missing month and day.

All listings will display the original dates as captured in the eCRF.

For analysis of efficacy data if one or both of the Day 6-8 or Day 13-15 photographs are missing then the photograph will be recorded as missing and the assessment of attenuation will not be made.

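### The individual peak titer counts the pre-vaccination Visit 1 sample, so an FAS subject with no later serum gets a baseline value as the vaccine peak

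*SAP*

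**What the plan says.** The SAP's General Definitions (Individual Peak Titer) and section 3.4 use the same window. In Group 1, "for each subject in Group 1 the individual maximum titer from Visit 1 to Visit 7 will be used"; in Group 2, "in Group 2 the individual maximum titer from Visit 1 to Visit 6 will be used". The definition gives the ELISA rule ("in Group 2 the individual maximum ELISA titer from Visit 1 to Visit 6 will be used") and extends it to the PRNT. Section 3.4 then runs the PRNT and ELISA non-inferiority tests on these peaks, with the same method and margins as the Peak Visit tests.

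Visit 1 is a baseline draw. Protocol 7.1 names it first among the visits at which "blood samples will be drawn prior to any scheduled vaccination". The Visit 1 task list in Protocol 4.2.2 also puts the antibody draw before randomization and vaccination.

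FAS membership (SAP 3.7.1) needs one dose and is open to any subject "for whom any post vaccination safety or immunogenicity data are available". Post-vaccination serum is not required. The same section adds: "The safety analysis and secondary supportive immunogenicity analyses will be performed on the FAS".

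SAP 3.8.1 sets a valid-case analysis for immunogenicity and rejects carrying observations forward, "since this could introduce an optimistic bias into the analysis".

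**The concern.** A vaccine peak should be a value the vaccine could have produced, and the Visit 1 titer cannot be. In most subjects this does no harm, because a later titer exceeds baseline and the maximum ignores Visit 1. It matters when there is no later titer. The stated maximum can still be computed from the one observed value, so the valid-case rule does not clearly remove the subject. A titer below the assay cut-off is scored 1, so the subject enters the test as a complete non-responder at log10 = 0. In substance this is baseline carried forward.

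The SAP closes this gap for the neighbouring endpoint: seroconversion is not calculated when the baseline or the relevant later titer is missing. The individual peak has no such rule.

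At stake is the FAS version of the individual-peak comparison. Such subjects in Group 2 lower the comparator GMT and favour non-inferiority. In Group 1 they lower the MVA-BN GMT and work against it. Neither effect is a vaccine response.

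**Working it through.** **Which analysis sets are exposed**
- PPS and ISS: not exposed to this route. SAP 3.7.2, item 9, treats missing Day 0 or peak-visit titers as a major violation, and the ISS is a subset of the PPS.
- FAS: exposed. Immediate adverse events are recorded on Day 0 after vaccination (Protocol 4.2.2), so safety data can exist without any later serum. After premature discontinuation, Protocol 4.2.6 aims for at least a closing safety visit and does not mention serum.
- Use of the FAS for this test is inferred. Section 3.4 names no set but says the analyses follow the PRNT and ELISA tests. SAP 3.2 and 3.10.7 run immunogenicity analyses on the PPS, FAS and ISS, and 3.7.1 assigns supportive ones to the FAS.

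**Reproducing the plan's sample size**
Inputs: margin 0.301, SD 0.866, true difference 0, one-sided 2.5%, power 90%.
- n = 2 × 0.866² × (1.960 + 1.282)² / 0.301² = 174 per group by the normal approximation.
- With the t-test, power is 89.8% at 174 and 90.01% at 175, so the stated 175 is confirmed.
- 175 / 0.80 = 218.75, rounded up to 219, against the stated 220.

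These are the inputs to the test that the individual-peak analysis copies.

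**Shift per baseline-only subject**
Assumptions: 220 per group in the FAS; SD 0.866; such subjects are seronegative (log10 = 0); mean log10 peak 2.2 for both assays. The documents give no expected peak for these assays. The 2.2 is the ACAM2000 Day 30 log10 mean in the prescribing information (Protocol Appendix IVc), from another trial, so a range is shown.
- Shift = mean / 220 = 2.2 / 220 = 0.0100 log10.
- Against the margins: 0.0100 / 0.301 = 3.3% (PRNT); 0.0100 / 0.176 = 5.7% (ELISA).
- For means of 1.5 to 2.5: 0.0068 to 0.0114, or 2.3-3.8% and 3.9-6.5% of the margins.

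**False non-inferiority (PRNT) with the true difference at -0.301, mean 2.2**
The nominal rate is 2.5%. The pooled-variance one-sided 97.5% limit was simulated with 40,000 runs per case. Each range is without and with titers floored at log10 = 0.
- All in Group 2: 4.0-4.4% (2 subjects), 6.3-6.7% (4), 22-24% (11).
- Four in each group: 2.4-2.6%.
- Total split at random between groups: 2.7-2.9% (4 subjects), 3.2-3.3% (11), 3.8-3.9% (22).

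**Power with a true difference of 0 and all such subjects in Group 1**
Power falls from about 95% to about 92-93% (2 subjects) and 85% (5).

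**After the fix**
With such subjects left out of one group, power is 95.3% (1 left out), 95.1% (5) and 94.8% (11). The 175 and 220 do not change.

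**The case against.** The case for leaving the text alone has several parts.

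1. Protocol 9.6 treats every secondary test as descriptive, and confirmatory testing is confined to the PPS. A reader might infer that a co-primary conclusion is at risk. It is not: neither co-primary analysis uses the individual peak. This stands.
2. FAS use is an inference. SAP 1.4.2 omits the individual-peak endpoint, and the planned tables cover non-inferiority at the Peak Visit only. This stands as a limit. However, Protocol 9.3.2 lists the endpoint and SAP 3.4 specifies its test.
3. Few subjects will qualify. A Group 2 subject would have to miss all five later draws (Visits 2 to 6). Group 1 subjects withdrawn after the first dose are still expected through Visit 4. The documents give no count. This stands.
4. A reader might take the 22-24% with 11 subjects as the expected harm. It requires all 11 to be in Group 2 and none in Group 1, and nothing in the documents supports that imbalance.
5. A programmer could treat such a subject as missing under 3.8.1. This is possible, but both SAP passages start the window at Visit 1, and following them gives a value. The wording needs settling.
6. A reader might expect the change to expose non-response in subjects who are seropositive at baseline. It does so only in part: a baseline antibody level that persists will also appear from Visit 2 onward. The ISS already addresses baseline seropositivity.

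**Conclusion.** The point holds in a limited form. As written, the rule can turn a pre-vaccination titer into a vaccine peak for an FAS subject without later serum, which conflicts with the SAP's own handling of missing titers and of seroconversion. Its reach is the secondary, descriptive individual-peak PRNT and ELISA tests, where they are run on the FAS.

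Under the stated assumptions the effect is about 0.010 log10 per subject. It biases the comparison materially only when such losses are unequal between groups. Two to four subjects all in Group 2 would raise false non-inferiority from 2.5% to about 4-6.5%; a random split of 4 to 22 gives about 3-4%. These rates rest on an assumed mean titer from another trial, an SD that is the upper confidence limit of a Day 42 estimate, and an unknown number of affected subjects. The correction is worth making because it is nearly free, not because a main result is in danger.

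**What to change.** In the SAP's General Definitions (Individual Peak Titer) and in section 3.4, define the individual peak as the maximum over post-vaccination samples only: Visit 2 to Visit 7 in Group 1 and Visit 2 to Visit 6 in Group 2. Add that it is not calculated if no post-vaccination titer is available. In the same edit, name the analysis sets for the individual-peak tests in 3.4, so that FAS use no longer has to be inferred.

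The cost is a few words in two places and in the derivation program, before the SAP is finalized ahead of database lock. No new data are needed, the sample size stays as it is, and any subjects without post-vaccination serum leave the FAS individual-peak analysis. Better handling of initially seropositive non-responders should not be claimed as a main benefit.
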